### 25 Background and rationale

- 26 Gout is the only form of arthritis that can potentially be "cured" with freedom from recurrent flares
- and disease progression provided long-term treat-to-target urate-lowering therapy (T2T-ULT) is prescribed and adhered with [1]. The goal of T2T-ULT is to achieve and maintain a serum urate
- 29 treatment target of <360 micromol/l [1].
- 30 The T2T strategy is a strategy that defines a treatment and applies tight control (for example, 31 monthly visits and respective treatment adjustments) to reach and maintain this target.
- 32 However, only a suboptimal proportion (around 40%) of patients with gout who start ULT will 33 achieve the serum urate treatment target within 12 months after ULT initiation [2]. Although not
- 34 recommended by international scientific societies, the fire-and-forget (FAF) approach is still widely
- 35 adopted by physicians treating gout patients. It mainly consists of prescribing treatment (e.g., ULT)
- 36 without further dose adjustment based on markers of its effectiveness (e.g., serum urate levels) [3].
- 37 Gout has traditionally been conceptualised as an intermittent inflammatory joint disease. However,
- 38 articular and systemic inflammation during the inter-critical period (i.e. between gout flares) has
- 39 been described recently [4]. Of greater concern, recent publications have demonstrated that flares
- 40 are temporally associated with subsequent cardiovascular events and death due to cardiovascular
- 41 events in the following 30-60 days [5,6]. As T2T-ULT is effective in preventing gout flares after the

42 first year of treatment, long-term T2T-ULT may prevent cardiovascular events and cardiovascular

- 43 mortality by reducing the number of flares [1].
- 44 There is, however, considerable controversy over whether T2T-ULT reduces the risk of adverse 45 cardiovascular events in people with gout, despite the potential for such an effect. Two systematic
- 46 literature reviews showed conflicting results, however, demonstrated several limitations in the
- 47 existing studies' ability to estimate effects on cardiovascular outcomes [7,8]. Firstly, included clinical
- 48 trials that recruited gout patients were underpowered and relatively short (<52 weeks) [7,8].
- 49 Secondly, observational studies that evaluated the association between ULT and cardiovascular
- 50 mortality compared people prescribed ULT with ULT non-initiators so confounding by indication and
- 51 healthcare-seeking behaviour biases may have affected the results [7,8]. Thirdly, no attempts were
- 52 made to ascertain whether the ULT initiators met the serum urate treatment target in all but one of 53 these studies [7–9].
- 54 A recent randomised controlled trial, the ALL-HEART study, showed that allopurinol does not 55 improve cardiovascular outcomes in patients with ischaemic heart disease, but gout was an 56 exclusion criterion for this study [10].
- 57

### 58 Aim

59 The main aim of this study will be to compare the risk of cardiovascular events among patients with 60 gout who initiate ULT and achieve the serum urate target of ≤360 micromol/l within 12 months from 61 ULT initiation with those who initiate ULT and do not have a recorded serum urate measurement of 62 ≤360 micromol/l within 12 months from ULT initiation.

63

## 64 Study design

65 This study will emulate an investigator-initiated, pragmatic, multicentre, two-arm, open-label, 66 randomised, superiority treatment strategy trial in gout patients initiating ULT for the first time using 67 a cloning, censoring, and weighting approach [11]. Cloning is used to assign people to treatment 68 duration strategies at time zero (i.e., at ULT initiation), eliminating immortal time bias and creating 69 two identical study arms at baseline. Then, a clone is censored when their available data (i.e., the 70 serum urate levels) are no longer compatible with the treatment strategy of the arm they entered, 71 but the follow-up continues for that individual in the arm of the compatible strategy. This induces 72 informative censoring [12], which will be addressed using inverse probability weighting [13].

- The emulation of target trials using real-world data can lead to high-quality evidence and high concordance with randomised controlled trials when closer emulation of trial design and measurements is adopted [14].
- 76

## 77 Study setting and data source

78 This study will be carried out in England and Sweden using data recorded in the course of routine

- 79 clinical care for people with gout managed in primary care. General Practices contributing to the
- 80 Clinical Practice Research Datalink (CPRD) Aurum and the Western Sweden Regional Healthcare
- 81 Database (VEGA) will be included in the study.
- 82 We will extract CPRD data for the period between 01/01/2007 and 29/03/2021 and VEGA data for
- 83 the period between 01/01/2007 and 31/12/2017 covering the periods over which linkage with

secondary-care data will be available. Indeed, the first recommendations for the management of
gout by the BSR and the EULAR were published in 2007 and 2006, respectively [15,16].

86 • Clinical Practice Research Datalink Aurum

CPRD database includes information from more than 38 million individuals, representative of the English population in terms of age, sex, and ethnicity [17]. CPRD data include information on demographic characteristics, lifestyle factors, diagnoses, primary care prescriptions, laboratory results, and immunisations [17]. Primary care data are linked to patient-level index of multiple deprivation (IMD) scores, hospitalization records via linkage with the Hospital Episode Statistics (HES) dataset, and information on date and causes of death via linkage with the Office for National Statistics (ONS) dataset.

Western Swedish Health Care Register

VEGA contains information about all healthcare contacts for both primary and secondary healthcare
 in western Sweden (~1.7 million inhabitants). All diagnoses given by physicians are registered
 according to the Swedish version of the International Classification of Disease (ICD) 10 codes.

98

94

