## 99 Eligibility criteria

- 100 The study population will consist of English and/or Swedish patients for whom research-quality data
- 101 are available, who are aged ≥18 years at first gout diagnosis in either primary care or secondary care
- 102 (whichever came first), are newly diagnosed with gout (defined as a new diagnostic code for gout
- 103 or gout flare at least 12 months after registration at their current general practice, and no prior
- 104 codes indicating history of gout to ensure only incident cases are included [18]) within the study 105 period, receive their first ULT prescription on or after the day of new gout diagnosis and have a
- 106 serum urate level >360 micromol/l before ULT initiation.
- Previous research has found a positive predictive value of gout diagnosis in electronic health records
  to be acceptable when compared to classification criteria for gout [19–21].
- 109

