## 157 Covariates

- We will collect the following covariates ascertained on or before ULT initiation to build the inverseprobability of censoring weighting as detailed above:
- demographics: age, sex (male or female), latest body mass index (BMI) available only in CPRD,
   socioeconomic deprivation assessed using the index of multiple deprivation (IMD) at patient
- socioeconomic deprivation assessed using the index of multiple deprivation (IMD) at patient
   level in CPRD and income and educational level in VEGA, latest smoking status (current, past, or
- non-smoker) available only in CPRD, latest alcohol intake (current, past, or no intake) available
   only in CPRD. Demographic variables will be ascertained within the 5 years before ULT initiation,
- 165 gout-related variables: gout duration (years), presence of subcutaneous tophi, number of anti-
- 166 inflammatory prescriptions (colchicine, NSAIDs, and corticosteroids) in 12 months before ULT
- 167 initiation, number of consultations in primary care for gout and number of hospitalisations for

- gout in the 12 months before ULT initiation, ULT molecule (i.e., febuxostat, allopurinol,
   uricosurics) and dose (high vs low starting dose), co-prescription of gout flare prophylaxis with
   colchicine and/or non-steroidal anti-inflammatory drugs on the date of ULT initiation (i.e.,
   prescription length ≥21 days);
- 172 general health and other cardiovascular comorbidities: Charlson Comorbidity Index [28], 173 cardiovascular comorbidities not included in the Charlson Comorbidity index (i.e., hypertension, 174 atrial fibrillation, and hypercholesterolemia), heart failure, diabetes with and without target 175 organ damage, chronic kidney disease (stage 3,4,5), dementia, peripheral vascular disease, 176 COPD, cancer, HIV/AIDS European Society of Cardiology cardiovascular risk (high/very high vs 177 moderate/low), history of cardiovascular events before ULT initiation, number of consultations 178 in primary care for any reason and number of hospitalisations for any cause in the 12 months 179 before ULT initiation,
- 180 medications (low-dose acetylsalicylic acid (ASA), non-ASA antiplatelet agents, statins, fibrates,
- other lipid-lowering agents, potassium-sparing diuretics, thiazides, loop diuretics, beta-blockers,
   calcium-channel blockers, angiotensin-converting enzyme inhibitors and angiotensin receptor

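### Extraction starts on 01/01/2007 with no separate look-back window, so for patients registered before 2007 and diagnosed in 2007 the tests for incident gout and first ULT have less than 12 months of data

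*Protocol*

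**What the plan says.** Study setting and data source sets the CPRD window, "We will extract CPRD data for the period between 01/01/2007 and 29/03/2021 and VEGA data for", and then the VEGA window, "the period between 01/01/2007 and 31/12/2017 covering the periods over which linkage with" secondary-care data is available. No other study dates are given.

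Eligibility criteria asks for a new code for gout "or gout flare at least 12 months after registration at their current general practice, and no prior" "codes indicating history of gout to ensure only incident cases are included [18]) within the study" period. The study period is not dated separately. The ULT condition is that patients "receive their first ULT prescription on or after the day of new gout diagnosis and have a" urate above 360 micromol/l before initiation. No ULT-free interval observed in the data is specified.

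Study design describes the target population as "gout patients initiating ULT for the first time using" cloning, with time zero at ULT initiation.

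Covariates asks for demographics from the 5 years before ULT initiation, gout-related and general health-care use from the preceding 12 months, gout duration, and "history of cardiovascular events before ULT initiation". Outcomes lists first-ever MACE as a secondary outcome.

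**The concern.** A test for no earlier code can only fail on a code that has been extracted. If extraction begins on the day entry can begin, the test has nothing to work on for the earliest entrants. The 12-month rule does not repair this, because someone who joined the practice years before 2007 satisfies it from the first day of the extract.

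Two kinds of misclassified patient matter differently. A person with long-standing gout who has never taken ULT still has a correct time zero, but is wrongly counted as incident and given too short a gout duration. A person who took ULT before 2007 has a false time zero, and the urate response over the following 12 months does not describe initiation. Cloning at a correct time zero is what the design relies on to remove immortal time bias, so the second group goes to its core.

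The same truncation reaches the censoring weights through the baseline covariates. It also reaches first-ever MACE, where an event before 2007 would not be visible and a recurrence could be counted as a first event.

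**Working it through.** No stated figure depends on this point, so there is nothing to reproduce. The check is calendar arithmetic.

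**Inputs.** Extraction windows (Study setting and data source): CPRD 01/01/2007 to 29/03/2021, VEGA 01/01/2007 to 31/12/2017. Washout (Eligibility criteria): 12 months from registration.

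**Look-back at entry.** Searchable look-back = diagnosis date minus 01/01/2007. Earliest permitted diagnosis = the later of 01/01/2007 and registration plus 12 months.

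| Registered | Earliest permitted diagnosis | Look-back in the extract |
|---|---|---|
| On or before 01/01/2006 | 01/01/2007 | 0 days |
| 01/07/2006 | 01/07/2007 | 31+28+31+30+31+30 = 181 days |
| 31/12/2006 | 31/12/2007 | 364 days |
| 01/01/2007 | 01/01/2008 | 365 days |

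For example, a patient registered in 2000 whose first extracted gout code is dated 01/02/2007 meets the registration rule with 31 days of searchable data. The shortfall affects everyone registered before 2007 and diagnosed during 2007. It affects nobody registered from 01/01/2007 onward.

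**Covariates.** These look back from ULT initiation. The 12-month counts are complete only for ULT started from 01/01/2008, and the 5-year demographics only for ULT started from 01/01/2012. History of cardiovascular events has no stated limit and is cut at 01/01/2007 for everyone. Gout duration needs no earlier data for a truly incident patient; it is wrong only for a patient misclassified as incident.

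**What the ULT order rule removes.** Covariates treats a medication as current if last prescribed within 60 days (CPRD) or 120 days (VEGA), a choice attributed to mean prescription length. A continuous ULT user would therefore be expected to show a prescription within the first two to four months of 2007. Such a patient passes only if both a gout code (on or before that prescription) and a urate above 360 micromol/l (before it) fall in that short interval. Patients restarting ULT after a gap are screened out less effectively.

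**Cost of delaying entry.** Counting both end dates, CPRD has 14×365 + 4 leap days + 88 days in 2021 = 5,202 days. VEGA has 11×365 + 3 = 4,018 days.

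- 12 months of look-back: 365/5,202 = 7.0% (CPRD); 365/4,018 = 9.1% (VEGA).
- 5 years of look-back (1,826 days): 35.1% and 45.4%.

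These are shares of calendar time, not of patients.

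**The case against.** The best answer is that the dates mark the linked study window and were never meant to cut off patient history. The protocol justifies them by secondary-care linkage and by the publication of gout guidelines in 2006 and 2007. The exclusion of earlier gout codes has no time limit, and a 5-year demographic window makes little sense without earlier records. The reference list also includes a CPRD gout cohort starting in 1997, which suggests that earlier primary-care data exist. This may well be the intention. But the text says that data are extracted from 01/01/2007, and nowhere says that earlier records will be searched. Gout may be diagnosed in either primary or secondary care, so earlier primary-care records alone would not settle the matter for hospital codes.

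A second answer stands in part: the order of gout code, raised urate and ULT prescription excludes many continuing users. It narrows the leak without closing it.

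A reader might go further in three ways that the document does not support:

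- That eligibility is stated to open on 01/01/2007, so that prevalent users do enter as new. The opening date is inferred from an undated study period, and misclassification is a risk of the literal reading.
- That the number of false new users can be estimated by applying a gout prevalence to the 1.7 million inhabitants covered by VEGA. Neither a prevalence nor the fraction passing the other criteria is given, and the 20,000 incident VEGA cases carry no ascertainment period.
- That VEGA is worse protected than CPRD because it records health-care contacts. The protocol does not say when VEGA records begin or how registration is handled there.

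**Conclusion.** The point holds as a defect in the stated rules, limited to patients registered before 2007 and diagnosed in 2007. For them the searchable history is under 12 months and can be 0 days, so some people with earlier gout or ULT could be classed as new. Separately, 5-year demographics are incomplete for ULT started before 2012, and cardiovascular history is cut at 01/01/2007.

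This rests on two assumptions: that the extraction dates mean what they say, and that the undated study period coincides with them. If earlier records are in fact searched, the defect is one of wording. Neither the number of patients affected nor the direction of any bias in the MACE comparison can be derived from the document. It is still worth correcting before analysis, because a correct time zero is central to the design and the correction is cheap.

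**What to change.** In Study setting and data source and in Eligibility criteria, define an entry window and a separate look-back window. Then adopt one of the following.

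1. **Preferred:** state that all available records before 01/01/2007 are used to exclude earlier gout codes and earlier ULT and to define baseline history. Say for each database whether this covers primary care, secondary care or both. This loses no entry time.
2. **Where earlier records cannot be obtained:** require at least 12 months of extracted data, free of gout codes and ULT, before the gout diagnosis, so that entry starts on 01/01/2008. In VEGA, express this as 12 months of register coverage.

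The second option makes at most 7.0% of CPRD and 9.1% of VEGA calendar time look-back only. It is a partial remedy. The 5-year demographics and cardiovascular history stay truncated for early entrants, and a patient whose last gout code or ULT prescription predates the clean 12 months would still pass. Requiring a full 5 years would cost 35.1% and 45.4% of calendar time, which is a strong reason to prefer the first option wherever the records exist. If the second is used, the protocol should acknowledge the remaining truncation, particularly for first-ever MACE.

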## 99 Eligibility criteria

- 100 The study population will consist of English and/or Swedish patients for whom research-quality data
- 101 are available, who are aged ≥18 years at first gout diagnosis in either primary care or secondary care
- 102 (whichever came first), are newly diagnosed with gout (defined as a new diagnostic code for gout
- 103 or gout flare at least 12 months after registration at their current general practice, and no prior
- 104 codes indicating history of gout to ensure only incident cases are included [18]) within the study 105 period, receive their first ULT prescription on or after the day of new gout diagnosis and have a
- 106 serum urate level >360 micromol/l before ULT initiation.
- Previous research has found a positive predictive value of gout diagnosis in electronic health records
  to be acceptable when compared to classification criteria for gout [19–21].
- 109

## 110 Treatment strategies

- 111 Intervention arm (T2T-ULT arm): To emulate ULT initiation aiming to achieve the serum urate target
- 112 of  $\leq$  360 micromol/l within 12 months after ULT initiation, serum urate target will be ascertained by
- 113 the earliest recorded serum urate measurement  $\leq$ 360 micromol/l within 12 months after ULT 114 initiation.
- 115 *Comparison arm (FAF-ULT arm):* Emulation of ULT initiation without an aim to achieve a serum urate
- 116 target will use patients without any recorded serum urate measurements or with serum urate >360
- 117 micromol/l within 12 months after ULT initiation.
- 118 Previous randomised controlled trials showed that the serum urate target can be achieved within 6
- 119 months from the first ULT prescription [1,22,23]. However, the proportion of patients achieving the
- 120 serum urate target in clinical practice is expected to be lower [2]. Therefore, we will allow 12 months
- 121 of grace after ULT initiation for participants to achieve the serum urate target.
- 122

# 123 Outcomes

- 124 Primary outcome: first major adverse cardiovascular event (MACE) in the 5 years following ULT
- 125 initiation. MACEs (i.e., either non-fatal acute myocardial infarction or non-fatal stroke (ischemic or

- 126 haemorrhagic) or cardiovascular death), will be ascertained using hospitalization, primary care, and
- 127 mortality records as follows:
- 128 Non-fatal myocardial infarction or non-fatal stroke documented in general practice records,
- hospitalization with non-fatal myocardial infarction or non-fatal stroke as the primary dischargediagnosis,
- cardiovascular death as the primary cause of death (i.e., the primary cause of death is fatal
   myocardial infarction, fatal stroke, cardiac arrest, heart failure, aortic dissection, or
   arrhythmias).
- Linkage across all data sources has been shown to improve the ascertainment of MACEs in CPRD[24–26]. The date of the MACE will be the earliest date of the above.
- Secondary outcomes: first-ever MACE, MACE requiring hospitalisation or leading to death, acute myocardial infarction, stroke, all-cause mortality, first gout flare requiring consultation in primary care or hospitalisation, and number of gout flares over the study period [5].
- 139 Negative control outcomes: acute bronchitis, cataract, and appendicitis over the study period. A
- 140 negative control outcome is a variable that has no plausible mechanism by which it can be caused
- 141 by the treatment of interest (i.e., colchicine prophylaxis) and is expected to share the same potential
- 142 sources of bias with the primary outcome (i.e., cardiovascular events) [27]. Negative control
- 143 outcomes s can serve as a diagnostic tool for assessing uncontrolled confounding [27].
- 144 Negative control outcomes and secondary outcomes will be ascertained in both primary care and 145 secondary care datasets, and mortality records. The date of the first record of these outcomes will
- 146 be the outcome date.
- 147

### 148 Follow up

- 149 People will be followed up from the first ULT prescription to the earliest date of a cardiovascular
- event, transfer out of the primary-care practice, death, 5 years from the first ULT prescription, studyend, and last consultation in primary care.
- Artificial censoring will be applied as follows: 1) clones assigned to the T2T-ULT arm will be censored at 12 months from ULT initiation if they do not achieve the serum urate target, 2) clones assigned to the FAF-ULT arm will be censored at the time they achieve the serum urate target within 12
- 154 to the FAF-OLT and will be censored at the time they achieve the seruin drate target v
- 155 months after the first ULT prescription.
- 156

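### The single follow-up rule stops at the first cardiovascular event; as written, it removes deaths after a non-fatal MI or stroke from all-cause mortality and truncates other secondary outcomes

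*Protocol*

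**What the plan says.** The protocol's Follow up section defines one observation period. "People will be followed up from the first ULT prescription to the earliest date of a cardiovascular" event is the first stop, and the list continues: "event, transfer out of the primary-care practice, death, 5 years from the first ULT prescription, studyend, and last consultation in primary care". The rule applies to people in general. It is not tied to a particular outcome, and the term for the cardiovascular stop is not tied to the MACE definition.

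The Outcomes section sets the primary outcome as "Primary outcome: first major adverse cardiovascular event (MACE) in the 5 years following ULT" initiation. The secondary list begins "Secondary outcomes: first-ever MACE, MACE requiring hospitalisation or leading to death, acute myocardial infarction, stroke, all-cause mortality, first gout flare" and ends with "number of gout flares over the study period". The negative controls have the same window: "Negative control outcomes: acute bronchitis, cataract, and appendicitis over the study period". For secondary and negative-control outcomes the section gives data sources and an outcome date ("Negative control outcomes and secondary outcomes will be ascertained in both primary care and" secondary care, and in mortality records), but no separate end of follow-up.

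The Statistical analysis section and the section on inverse probability of censoring weighting add no outcome-specific stop and no competing-event rule.

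**The concern.** A stop at the first cardiovascular event is natural when that event is the outcome. For an outcome that can occur later, it discards the observation time in which that outcome is most likely.

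- **All-cause mortality.** A patient who has a non-fatal MI in year 1 and dies in year 2 is not counted as a death. The outcome becomes death without an earlier non-fatal cardiovascular event.
- **MI and stroke separately.** A stroke ends follow-up for MI, and the reverse.
- **Hospitalised or fatal MACE.** An earlier event recorded only in general practice ends follow-up before a later hospitalised or fatal event.
- **Flares and negative controls.** Events after a cardiovascular event are dropped, although the Outcomes section sets the flare count and the negative controls over the study period.

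The stop depends on prognosis. The Background section expects reaching the urate target to reduce flares and, through them, cardiovascular events and cardiovascular death, so the stop may also depend on arm. The weights are aimed at departure from the assigned strategy during the grace period. They are modelled from time, baseline covariates and ULT days covered, and nothing in them addresses a stop at a cardiovascular event.

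**Working it through.** The protocol gives no figure for this loss. Its power statement concerns MACE and does not bear on the point, so the check sizes what the rule cuts off.

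**Inputs from the protocol (Feasibility count and sample size considerations):** MACE rate λ = 0.017 per year in the unexposed; 14,000 + 30,000 = 44,000 people. Horizon 5 years (Outcomes).

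**Assumed inputs, not in the documents:** share f of first MACEs that are non-fatal, 0.6 to 0.8; other mortality μ0, 0.01 to 0.03 per year; mortality after a non-fatal event μp, 0.05 to 0.15 per year. Constant rates, full 5-year follow-up, no other exits.

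**Step 1: people and person-time affected, from protocol inputs alone.**
- First MACE by 5 years: 1 − exp(−0.017 × 5) = 0.0815, about 8.1%, or about 3,590 of 44,000.
- Mean time before the stop: 0.0815 / 0.017 = 4.793 years of 5. Person-time after the stop: 1 − 4.793/5 = 4.1%. This is an upper bound, because some first MACEs are fatal and some people die afterwards.

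**Step 2: deaths dropped (illness-death model).** Let a = λ + μ0 and A = (1 − e^(−5a))/a.
- Deaths kept = [λ(1 − f) + μ0] × A.
- Deaths dropped = λf × [A − (e^(−5μp) − e^(−5a))/(a − μp)].

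Mid-values (f = 0.7, μ0 = 0.02, μp = 0.10): kept 0.1146, dropped 0.0119; share 0.0119/0.1265 = 9.4%.

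Across the grid:
- Lowest share (f = 0.6, μ0 = 0.03, μp = 0.05): kept 0.1640, dropped 0.0054; 3.2% of deaths, about 240 per 44,000.
- Highest share (f = 0.8, μ0 = 0.01, μp = 0.15): kept 0.0627, dropped 0.0192; 23.5% of deaths, about 850 per 44,000.

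The range is therefore about 0.5 to 1.9 percentage points of 5-year deaths, or 3 to 24% of all deaths. It depends strongly on μ0. With μ0 fixed at 0.03 and μp at 0.08 to 0.15, the share is only 5 to 11%.

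**Step 3: effect on the arm contrast.** Suppose, for illustration, that reaching target cuts the MACE rate by 15% (λ = 0.01445) and changes nothing else. A Kaplan-Meier analysis censored at the non-fatal event estimates 1 − exp(−5[λ(1 − f) + μ0]). With f = 0.7, μ0 = 0.03, μp = 0.10:
- True 5-year mortality (kept + dropped): 0.1681 against 0.1639, a difference of 0.42 points.
- Under the rule: 1 − exp(−0.1755) = 0.1610 against 1 − exp(−0.1717) = 0.1578, a difference of 0.32 points.
- Lost: (0.42 − 0.32)/0.42, about a quarter.

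With μ0 kept at 0.03 and μp between 0.08 and 0.15, the loss runs from about 11% (0.48 to 0.43 points; f = 0.6, μp = 0.08) to about 47% (0.41 to 0.22 points; f = 0.8, μp = 0.15). The pull is always towards no effect.

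**The case against.** The best defence is that the rule was written with only the primary outcome in mind. The stop matches first MACE within 5 years, and the section never says that it governs secondary or negative-control outcomes. The Outcomes section gives the flare count and negative controls their own window, and detail on censoring by outcome is often left to a SAP. Part of this stands: for flares and negative controls the two sections conflict, and a stop at MACE is not plainly fixed. It does not rescue all-cause mortality. The only rule stated applies to everyone, the study-period wording does not clearly attach to mortality, and no other text lets follow-up continue.

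A reader might infer that every secondary analysis loses heavily, or that the negative-control check is invalidated. The documents do not support either. At most about 4% of person-time follows a first MACE. Negative controls are meant to share the primary outcome's sources of bias, so using the same window for them is defensible.

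Analysing MI and stroke each up to the other component is a recognisable cause-specific estimand. It would be acceptable if declared, but the protocol does not declare it.

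Finally, all mortality inputs are assumed, and the pull towards no effect operates only if reaching target reduces MACE.

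**Conclusion.** The point holds as a fault in the stated rule for outcomes other than the primary outcome and first-ever MACE. The main harm is to all-cause mortality, followed by separate MI and stroke and by hospitalised or fatal MACE. Cardiovascular deaths that are themselves the first event, and deaths with no earlier event, are still counted.

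The dropped share of roughly 3 to 24% of 5-year deaths rests on the protocol's MACE rate and on assumed mortality inputs, so it shows scale and is not a prediction. For flares and negative controls the issue is mainly an inconsistency between sections. The authors may not have intended the stop to apply beyond MACE; the sentence needs correcting in either case. This should be fixed, but it does not threaten the primary result.

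**What to change.** In the Follow up section:

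- Limit the stop at a cardiovascular event to the outcomes it fits (the primary outcome and first-ever MACE), and tie the term to the MACE definition.
- For each other outcome, end follow-up at the first occurrence of that outcome. For the number of flares, do not stop at an event.
- Keep all the other stops for every outcome: transfer out, death, 5 years, study end and last consultation.
- Follow all-cause mortality through non-fatal events to death.
- Treat death as a competing event for non-fatal outcomes.
- Reconcile the study-period window for flares and negative controls in the Outcomes section with the Follow up section, including the 5-year limit.

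The cost is a sentence or two of protocol text and outcome-specific end dates in the analysis files. The linked data already hold the event and death dates, and the primary analysis does not change.

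### Read literally, follow-up ends at the patient's last primary-care consultation, so deaths after that contact are not counted and fatal outcomes are under-counted

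*Protocol*

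**What the plan says.** The Follow up section sets one rule for the end of observation. Each person is observed from ULT initiation until the first of several dates. Besides a cardiovascular event and leaving the practice, the list names "death, 5 years from the first ULT prescription, studyend, and last consultation in primary care". Death and the last primary-care consultation are separate items in the list, and whichever comes first applies. No exception is made for deaths or hospital events after the last consultation, and the term is not defined.

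The Outcomes section relies on fatal events. The third component of the primary MACE is "cardiovascular death as the primary cause of death", and events come from hospital, primary-care and mortality records. The secondary outcomes include "MACE requiring hospitalisation or leading to death, acute myocardial infarction, stroke, all-cause mortality". The horizon is 5 years from the start of ULT.

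For CPRD, the Study setting and data source section describes a linkage to national death records: "information on date and causes of death via linkage with the Office for National". Such a date and cause of death do not depend on any contact with the practice.

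**The concern.** A patient who dies attended the last consultation on or before the day of death. If it was earlier, the earliest-date rule ends follow-up there and the later death is not an event. The separate death item can then bind only when some consultation record carries the date of death or a later one. The rule thus discards deaths that the linkage was set up to find.

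Three consequences follow.

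- The primary MACE shifts towards non-fatal infarction and stroke.
- All-cause mortality and MACE leading to death are under-counted. For all-cause mortality, every component is affected.
- The end date is set with knowledge of the future. A person is certain to be alive up to the last contact, so the counted person-time is conditioned on survival.

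The planned weights do not repair this. The Statistical analysis section introduces them to deal with artificial censoring in the cloned arms, not with this end date. Even if they were extended to it, a person whose last record precedes death is never under observation at death. The deaths that remain visible are those with a same-day or later record, which is a selected set.

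**Working it through.** **1. The plan's own figures.** The protocol gives no figure for deaths lost through this rule. The nearest is the sample-size statement in Feasibility count and sample size considerations: 17 MACE per 1,000 person-years in the unexposed, a difference of 1 per 1,000, 14,000 exposed against 30,000 unexposed, alpha 0.025 and power above 99%. A Wald test of two Poisson rates, with a full 5 years for everyone, gives

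SE = √(0.017/150,000 + 0.016/70,000) = 0.000585; z = 0.001/0.000585 = 1.71; power = Φ(1.71 − 2.24) ≈ 0.30 (two-sided 0.025), or 0.40 (one-sided 0.025).

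So the stated power is not reproduced. That is a separate matter; 0.30 serves below only as a baseline.

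**2. Deaths counted.** Follow-up ends at min(last consultation, death, 5 years), leaving the other end dates aside. A death within 5 years counts only if the last consultation record is dated on or after the death. With q the share of deaths that have such a record,

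share of deaths counted = q.

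This does not depend on how often patients consult. The documents do not give q. For q = 0, 0.1, 0.3 and 0.5, the share counted is 0%, 10%, 30% and 50%.

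**3. MACE kept.** With f the share of first MACE that is cardiovascular death (also not given), and all non-fatal events kept,

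share of MACE kept = 1 − f(1 − q).

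| f | q = 0 | q = 0.1 | q = 0.3 | q = 0.5 |
|---|---|---|---|---|
| 0.2 | 80% | 82% | 86% | 90% |
| 0.3 | 70% | 73% | 79% | 85% |
| 0.4 | 60% | 64% | 72% | 80% |

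Applied to 17 per 1,000 person-years, with person-time taken as roughly unchanged, the ends of this range are 17 × 0.60 = 10.2 and 17 × 0.90 = 15.3.

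**4. Check by simulation.** Assumed inputs: death hazard 0.03 per year, non-fatal event hazard 0.011 per year, an 8-year data window, 2, 6 or 12 consultations per year, and consultations independent of events.

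- Deaths counted matched q at every consultation rate: 0%, about 10%, about 30% and about 50%.
- The true 5-year risk of death was about 14% (1 − e^(−0.15) = 0.139). At q = 0 the observed death rate was 0. At q = 0.3 it was about 9 per 1,000 person-years, against a true 30.
- Between 98.6% and 99.9% of non-fatal events were kept.

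The zero at q = 0 follows by construction and is not evidence about real records. The simulation confirms the formula and shows that non-fatal events are little affected.

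**5. Effect on power, for illustration.** At f = 0.3 and q = 0, both rates are multiplied by 0.7. Then z = 1.71 × √0.7 = 1.43, and power falls from 0.30 to Φ(1.43 − 2.24) ≈ 0.21 (two-sided 0.025). This assumes the same relative effect on fatal and non-fatal events.

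**The case against.** The strongest defence is that the term is undefined and may have been meant harmlessly. Death is its own item in the list and would be nearly redundant if the patient's own last contact usually came first. The protocol also obtains linked causes of death and counts cardiovascular death from mortality records. Both suggest that the last consultation was intended as a loss-to-follow-up date for people without an event, or as the last date of data capture. On the data-capture reading, deaths before that date are kept.

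This makes it plausible that the authors did not intend the loss, but it does not rescue the text. Elsewhere the protocol uses consultation for patient contacts, as in the counts of primary-care consultations among the covariates and the flare outcome. Study end is already a separate item. Whichever meaning was intended, an analyst who follows the sentence as written will censor before most recorded deaths unless q is high.

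Two stronger readings are tempting and should be resisted. A reader might infer that virtually every fatal event is lost and that all-cause mortality cannot be estimated. That needs q close to zero, and the documents are silent on q. A reader might also infer a bias between arms, because patients monitored to target are seen more often. Contact with care may well differ by arm. However, the share of deaths counted does not change with consultation frequency; a difference would have to come through q, and nothing in the documents gives its size or direction.

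**Conclusion.** Wrong as written. The rule for the end of follow-up contradicts the primary outcome's cardiovascular-death component, two secondary outcomes and the use of linked mortality records. This is a rule that the protocol states, not detail left for an analysis plan.

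The direction is clear: fatal outcomes are under-counted, possibly almost entirely, and the end date looks ahead. The size is not known from the documents. It rests on the assumed q and f and on taking the last consultation to be the patient's own last contact. Even at q = 0.5, half of all deaths drop out of the mortality outcome. MACE is under-counted and shifted towards non-fatal events; it is not lost. A complete loss of fatal events and a bias between the arms are both possible, but the documents establish neither.

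**What to change.** In Follow up, remove the patient's last primary-care consultation as an end date. Follow each person to the earliest of first event, transfer out, death, 5 years, and the end of data capture or linkage in the database concerned. The protocol already gives extraction ends chosen to match linkage: 29/03/2021 for CPRD and 31/12/2017 for VEGA. A practice's last collection date can be used where one exists; the protocol documents none, including for VEGA. State that linked deaths and hospital events count up to and including the end date.

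If a practice-level last data date was what the authors meant, name it in place of the last consultation.

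The cost is one sentence and a different date variable. The extraction-end version uses only dates already in the protocol. Whether a practice-level date is available would need checking separately in each database.
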